### 6.3 Outcome variables and study follow-up:

#### 6.3.1 Outcome variables

Primary Effectiveness outcomes of interest: (definitions provided in **Appendix A**):

- **Primary Outcome:** VTE and cause-specific mortality
- **Secondary Outcome:** Individual components
  - Hospital admission for VTE (principal diagnosis position)
  - Cause-specific mortality
    - Inpatient mortality identified using discharge status codes from hospitalization for VTE

Safety outcome of interest:

1. Major bleeding

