#### 6.3.2 Study follow-up

Both as-treated (AT) and intention-to-treat (ITT) analyses will be conducted with treatment defined as the index drug on the day of cohort entry. Because adherence in the real-world databases is expected to be much worse than in the trial, the AT analysis is the **primary** analysis, as it targets the relative hazard of outcomes on treatment.

For the AT analyses, the follow-up will start the day after initiation of apixaban and comparator and will continue until the earliest date of the following events:

- The first occurrence of the outcome of interest, unless otherwise specified for selected outcomes,
- The date of end of continuous registration in the database,
- End of the study period,
- Measured death event occurs,
- Nursing home admission

- Nursing home admissions are considered a censoring event because the data sources utilized typically provide little to no data on a patient, particularly on drug utilization, after admission. We will utilize this as an exclusion reason for cohorts for the same reason.
- The date of drug discontinuation, defined as the date of the last continuous treatment episode of the index drug (apixaban and comparator) plus a defined grace period (i.e., 10 days after the end of the last prescription's days' supply in main analyses).
- The date of augmentation or switching from exposure to comparator or vice versa or augmentation/switching to any other NOAC (e.g. switching from apixaban to rivaroxaban would be a censoring event);
  - A dosage change on the index treatment does not fulfill this criterion
  - An added treatment that is not part of the exposure or comparator group does not fulfill this criterion
- Treatment of current episode of VTE with thrombectomy, insertion of caval filter, or use of fibrinolytic agent (streptokinase, alteplase, reteplase, tenecteplase)

For the intention-to-treat (ITT) analyses, the censoring based on the augmentation/switching and treatment discontinuation will be replaced with a maximum allowed follow-up time of 365 days.

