| The primary efficacy outcome was recurrent symptomatic venous thromboembolism or death related to venous thromboembolism.                                                                                                                                                                                                                                                                                                                                                                            | Measured 1 day after drug initiation                                                                                                                                                                                                                        | Fang MC, Fan D, Sung SH, et al. Validity of Using Inpatient and Outpatient Administrative Codes to Identify Acute Venous Thromboembolism: The CVRI VTE Study. Med Care . 2017;55(12):e137-e143.                                                                           | Can be replicated in claims
Can be intermediately measured in claims                                                                                                                                                                                                                                                                                                                                                                                                                                            |

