| • Acute symptomatic proximal deep vein thrombosis (DVT) with evidence of proximal thrombosis that involves at least the popliteal vein or a more proximal vein, demonstrated by imaging with: - compression ultrasound (CUS), including grey-scale or color-coded Doppler, OR - ascending contrast venography                                                                                                                                                                                        | Measured 180 days prior to and including day of drug initiation in any diagnosis position and in an inpatient or ED care setting

Deep vein thrombosis (DVT):
ICD-9 Dx: 451.xx, 453.xx
ICD-10 Dx: I26.xx, I80.xx, I81.xx, I82.xx, I26.xx |                                                                                                                                                                                                                                                                                  |                                                                                                                                                                                                                                                                                                                                                                                                                                                                                                                    |

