| • Acute symptomatic PE with evidence of thrombosis demonstrated by imaging as follows:
- an intraluminal filling defect in segmental or more proximal branches on spiral computed tomography (CT) scan; or
- an intraluminal filling defect or a sudden cutoff of vessels more than 2.5 mm in diameter on the pulmonary angiogram; or
- a perfusion defect of at least 75% of a segment with a local normal ventilation result (high probability) on ventilation/perfusion lung scan (VPLS) | Measured 180 days prior to and including day of drug initiation in any diagnosis position and in an inpatient or ED care setting

Pulmonary embolism (PE):
ICD-9 Dx: 415.xx
ICD-10 Dx: I26.xx                                            |                                                                                                                                                                                                                                                                                  |                                                                                                                                                                                                                                                                                                                                                                                                                                                                                                                    |

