# Appendix A

|                                             |                                                                                            |
|---------------------------------------------|--------------------------------------------------------------------------------------------|
| 453.9                                       | EMBOLISM AND THROMBOSIS OF UNSPECIFIED SITE                                                |
| ICD-10 Dx inpatient primary position |                                                                                            |
| PE                                   |                                                                                            |
| I26.0                                       | Pulmonary embolism with acute cor pulmonale                                                |
| I26.01                                      | Septic pulmonary embolism with acute cor pulmonale                                         |
| I26.02                                      | Saddle embolus of pulmonary artery with acute cor pulmonale                                |
| I26.09                                      | Other pulmonary embolism with acute cor pulmonale                                          |
| I26.9                                       | Pulmonary embolism without acute cor pulmonale                                             |
| I26.99                                      | Other pulmonary embolism without acute cor pulmonale                                       |
| DVT                                  |                                                                                            |
| I80.1                                       | Phlebitis and thrombophlebitis of femoral vein                                             |
| I80.10                                      | Phlebitis and thrombophlebitis of unspecified femoral vein                                 |
| I80.11                                      | Phlebitis and thrombophlebitis of right femoral vein                                       |
| I80.12                                      | Phlebitis and thrombophlebitis of left femoral vein                                        |
| I80.13                                      | Phlebitis and thrombophlebitis of femoral vein, bilateral                                  |

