## Appendix A

|         |                                                                                                 |
|---------|-------------------------------------------------------------------------------------------------|
| I82.441 | Acute embolism and thrombosis of right tibial vein                                              |
| I82.442 | Acute embolism and thrombosis of left tibial vein                                               |
| I82.443 | Acute embolism and thrombosis of tibial vein, bilateral                                         |
| I82.449 | Acute embolism and thrombosis of unspecified tibial vein                                        |
| I82.49  | Acute embolism and thrombosis of other specified deep vein of lower extremity                   |
| I82.491 | Acute embolism and thrombosis of other specified deep vein of right lower extremity             |
| I82.492 | Acute embolism and thrombosis of other specified deep vein of left lower extremity              |
| I82.493 | Acute embolism and thrombosis of other specified deep vein of lower extremity, bilateral        |
| I82.499 | Acute embolism and thrombosis of other specified deep vein of unspecified lower extremity       |
| I82.4Y  | Acute embolism and thrombosis of unspecified deep veins of proximal lower extremity             |
| I82.4Y1 | Acute embolism and thrombosis of unspecified deep veins of right proximal lower extremity       |
| I82.4Y2 | Acute embolism and thrombosis of unspecified deep veins of left proximal lower extremity        |
| I82.4Y3 | Acute embolism and thrombosis of unspecified deep veins of proximal lower extremity, bilateral  |
| I82.4Y9 | Acute embolism and thrombosis of unspecified deep veins of unspecified proximal lower extremity |
| I82.4Z  | Acute embolism and thrombosis of unspecified deep veins of distal lower extremity               |
| I82.4Z1 | Acute embolism and thrombosis of unspecified deep veins of right distal lower extremity         |
| I82.4Z2 | Acute embolism and thrombosis of unspecified deep veins of left distal lower extremity          |
| I82.4Z3 | Acute embolism and thrombosis of unspecified deep veins of distal lower extremity, bilateral    |
| I82.4Z9 | Acute embolism and thrombosis of unspecified deep veins of unspecified distal lower extremity   |
| I82.5   | Chronic embolism and thrombosis of deep veins of lower extremity                                |

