# Appendix B

|                                                                                            |               |               |           |               |               |           |               |               |           |               |               |         |
|--------------------------------------------------------------------------------------------|---------------|---------------|-----------|---------------|---------------|-----------|---------------|---------------|-----------|---------------|---------------|---------|
| Non-Frailty; n (%)                                                                         | 206 (42.0%)   | 210 (42.9%)   | -0.02     | 581 (42.1%)   | 583 (42.2%)   | 0.00      | 57 (3.4%)     | 47 (2.8%)     | 0.03      | 844 (23.6%)   | 840 (23.5%)   | 0.00    |
| Frailty Score (mean): Empirical Version
365 days, v2                                    |               |               |           |               |               |           |               |               |           |               |               |         |
| ...mean (sd)                                                                               | 0.18 (0.06)   | 0.18 (0.06)   | 0.00      | 0.15 (0.05)   | 0.15 (0.05)   | 0.00      | 0.10 (0.07)   | 0.10 (0.08)   | 0.00      | 0.13 (0.06)   | 0.13 (0.07)   | 0.00    |
| Healthcare Utilization                                                                     |               |               |           |               |               |           |               |               |           |               |               |         |
| Any hospitalization; n (%)                                                                 | 438 (89.4%)   | 453 (92.4%)   | -0.10     | 1,379 (99.9%) | 1,380 (99.9%) | 0.00      | 1,564 (92.1%) | 1,555 (91.5%) | 0.02      | 3,381 (94.7%) | 3,388 (94.9%) | -0.01   |
| Any hospitalization within prior 30 days; n (%)                                            | 374 (76.3%)   | 364 (74.3%)   | 0.05      | 1,287 (93.2%) | 1,302 (94.3%) | -0.05     | 1,204 (70.9%) | 1,229 (72.3%) | -0.03     | 2865 (80.3%)  | 2895 (81.1%)  | -0.02   |
| Any hospitalization during prior 31-180 days; n (%)                                        | 101 (20.6%)   | 121 (24.7%)   | -0.10     | 185 (13.4%)   | 166 (12.0%)   | 0.04      | 565 (33.3%)   | 546 (32.1%)   | 0.03      | 851 (23.8%)   | 833 (23.3%)   | 0.01    |

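### The primary outcome has no rule separating continued care of the index VTE from a recurrence, so a transfer or next-day admission for the same clot would count as an event

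*Combined protocol and SAP*

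**What the plan says.** The endpoint being emulated is recurrent symptomatic VTE or VTE-related death (Section 1.3 and Appendix A, Primary Outcome). The replication uses these rules:

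- **Index VTE** (Appendix A, Inclusion Criteria, same wording for DVT and PE): "Measured 180 days prior to and including day of drug initiation in any diagnosis position and in an inpatient or ED care setting". An ED diagnosis on day 0 qualifies.
- **Outcome** (Section 6.3.1): "Hospital admission for VTE (principal diagnosis position", combined with inpatient death during a VTE hospitalization. The Appendix A code lists carry the same restriction, for example "ICD-10 Dx inpatient primary position".
- **Start of capture**: "Measured 1 day after drug initiation" in Appendix A. Section 6.3.2 agrees for the primary as-treated analysis: "the follow-up will start the day after initiation of apixaban and comparator".

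The visible text gives no minimum gap from the index diagnosis, no episode or transfer linkage, no requirement that the event be new, and no statement of which date an outcome event carries. The outcome code list also accepts codes such as "Chronic embolism and thrombosis of deep veins of lower extremity". Section 13.2, reserved for sensitivity analyses, lists none.

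**The concern.** The two definitions meet with no gap. Take a patient diagnosed in the ED and dispensed the drug on day 0, then admitted or transferred on day 1 with the same clot as principal diagnosis. This patient satisfies the cohort entry rule and then the outcome rule, and enters the primary analysis as a recurrence. Such an event says nothing about whether the drug prevents recurrence.

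The plan itself accepts that care of the index episode can run past day 0: Section 6.3.2 censors follow-up when the current VTE episode is treated by thrombectomy, caval filter or fibrinolysis. It does not define that episode or apply the idea to the outcome.

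With about 98 events expected in total, and about 13 in Optum, a handful of misclassified events matters. They would also already be part of the observed risk on which the power table in Section 10 is built.

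**Working it through.** **1. Reproduce the plan's power.** Inputs from Section 10 (pooled): 7,140 matched patients, risk 13.74 per 1,000, HR 0.84, margin 1.8, two-sided alpha 0.05.

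- Expected events: E = 7,140 × 13.74/1,000 = 98.1036, as printed.
- Power = Φ(√(E/4) × (ln 1.8 − ln 0.84) − 1.96) = 0.9652, as printed (0.965194245). The three single-database powers reproduce as well.

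**2. Who is exposed.** Appendix B, PS-matched table, pooled columns, patients with any hospitalization at baseline: 3,381 warfarin and 3,388 apixaban, of 3,570 each.

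- None: (3,570 − 3,381) + (3,570 − 3,388) = 189 + 182 = 371, and 371/7,140 = 5.2%.
- The row does not state its window. If it is 180 days, as the companion rows for 0–30 and 31–180 days suggest, these patients' qualifying VTE was ED-only.
- This is not a strict ceiling. A patient hospitalized earlier for another reason can also have an ED index, and an inpatient index stay can be followed by a contiguous readmission. Nor are all 371 at risk, since the ED visit may be weeks before dispensing.

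**3. How many events.** The rate of immediate admission for the same clot is not in the documents. Assuming 1% and 2%:

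- 371 × 0.01 = 3.7 events; 3.7/98.1 = 3.8%.
- 371 × 0.02 = 7.4 events; 7.4/98.1 = 7.6%.

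**4. Effect on the HR.** Let a share f of all events be index clots split equally between arms, with the rest divided HR : 1. Then

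observed HR = [(1 − f) × HR/(1 + HR) + f/2] / [(1 − f)/(1 + HR) + f/2].

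The one-sided error at a true HR of 1.8 is Φ(√(E/4) × (ln 1.8 − ln observed HR) − 1.96).

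| f | True 1.8 reads | One-sided error at 1.8 | True 0.84 reads |
|---|---|---|---|
| 0 | 1.80 | 0.025 | 0.84 |
| 3.8% | 0.6375/0.3625 = 1.76 | 0.033 | 0.846 |
| 7.6% | 0.6321/0.3679 = 1.72 | 0.042 | 0.851 |

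Rounding the upper share to 8% gives 1.71.

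**5. If those events are removed.** 98.1 − 3.7 = 94.4 events gives power 0.959; 98.1 − 7.4 = 90.7 gives 0.952, both by the step 1 formula at HR 0.84.

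**The case against.** The outcome definition does filter. It needs an inpatient stay with VTE as principal diagnosis, which is narrower than the index rule ("in any diagnosis position and in an inpatient or ED care setting"). If events are dated by admission, an index stay that began by day 0 drops out. That reduces the problem but does not remove it: a day-1 admission for the index clot will often carry VTE as principal diagnosis, and event dating is not stated.

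The database figures also show no sign of a large effect. Matched patients with no baseline hospitalization number 89/980 (9.1%) in Optum, 279/3,398 (8.2%) in Medicare and 3/2,762 (0.1%) in MarketScan. The primary-outcome risks are 12.93, 14.66 and 13.13 per 1,000 (Section 9). MarketScan has almost no such patients, yet its risk is slightly above Optum's. Counts are small and the populations differ, so this does not exclude the problem, but it gives no support for a large one.

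A reader might instead start from the row "Any hospitalization within prior 30 days; n". It leaves 7,140 − 2,865 − 2,895 = 1,380 patients (19.3%), and 1–2% of them gives 14–28 events, or 14–28% of those expected. The documents do not support that base. It includes patients whose index VTE lies 31 to 180 days back, which cannot produce a contiguous next-day admission.

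Finally, Appendix A refers to an external folder for further or missing details, and the design diagram is not shown. A rule could exist there. What is established is its absence from the visible text; a rule that defines the primary outcome belongs in the registered document.

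**Conclusion.** The point holds as a defect in a stated rule: read literally, the plan counts a contiguous admission for the index clot as a recurrence. Its likely size is modest and uncertain. Under the assumptions above (a 180-day covariate window, 1–2% admitted at once, equal split between arms), it amounts to about 4–7 events, or 4–8% of 98.1, and a true HR of 1.8 would read about 1.72–1.76.

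A reader might infer that such events always favour non-inferiority and hide disagreement with the trial. That does not follow. Balanced contamination pulls the HR toward 1, which favours non-inferiority only when the true HR exceeds 1. At the planning value of 0.84 it moves the estimate toward the margin and away from the trial result. Unbalanced contamination could bias either way, and the documents give no information on balance.

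**What to change.** Add one outcome rule to Section 6.3.1 and Appendix A:

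- Date each outcome event by its admission date.
- Do not count a VTE admission that is contiguous with the index VTE encounter (a transfer, or an admission within 1 day of the index ED visit or discharge). Link it to the index episode.

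Then recompute the overall risk in Section 9 and the power tables in Section 10, and report how many events the rule removes, overall and per database. This can be done before any comparison by treatment group.

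This rule defines an episode and is not a blanking period. A later start of outcome capture is optional and should be no more than a sensitivity analysis, because it would also discard genuine early events.

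The cost is one rule and one rerun of the risk and power figures. A rare true recurrence in the first day or two may be missed, and the expected event count may fall slightly.

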### 5.2 Important steps for cohort formation

New use of apixaban, exposure, and warfarin, comparator, is defined as no use of either therapy in the 180 days prior to index date.

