### 6.2 Covariates:

- Age
- Sex
- Combined Comorbidity Index (CCI), measured over the baseline covariate assessment period, defined as 180 days prior to and including index date

Covariates listed above represent only a small subset of covariates that will ultimately be controlled for in the design and analysis. We use the covariates above only for initial feasibility analyses to judge whether there is likely to be sufficient overlap between treatment groups to proceed with the study. Remaining covariates are defined only after the study has passed the initial feasibility analysis and the initial power assessment and are listed in Table 1 (**Appendix B**).

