## 9. Balance Assessment

**Action report links:**

Optum: <https://bwh-dope.aetion.com/projects/details/1484/results/64541/result/0>

Marketscan: <https://bwh-dope.aetion.com/projects/details/1481/results/64542/result/0>

Medicare: <https://bwh-dope.aetion.com/projects/details/1483/results/64543/result/0>

Date conducted: 1/19/2021

After review of initial feasibility and power analyses, complete creation of the remaining covariates from Section 6.2. Again, using the dummy outcome of a 90-day gap in database enrollment, complete a 1:1 PS-matched analysis. The PS should include the complete list of covariates.

- Provide plot of PS distributions stratified by treatment group.

Note- Please refer to **Appendix B**.

- Report covariate balance after matching.

Note- For Table 1, please refer to **Appendix B**.

- Report reasons for censoring by treatment group.

|  | Overall | Referent | Exposure |
|--|---------|----------|----------|
|--|---------|----------|----------|

|                                                                                                                               |                |                |                |
|-------------------------------------------------------------------------------------------------------------------------------|----------------|----------------|----------------|
| Dummy outcome                                                                                                                 | 67 (0.94%)     | 25 (0.70%)     | 42 (1.18%)     |
| Death                                                                                                                         | 103 (1.44%)    | 49 (1.37%)     | 54 (1.51%)     |
| Start of an additional exposure                                                                                               | 232 (3.25%)    | 175 (4.90%)    | 57 (1.60%)     |
| End of index exposure                                                                                                         | 4,701 (65.84%) | 2,202 (61.68%) | 2,499 (70.00%) |
| Specified date reached                                                                                                        | 857 (12.00%)   | 424 (11.88%)   | 433 (12.13%)   |
| End of patient enrollment                                                                                                     | 425 (5.95%)    | 198 (5.55%)    | 227 (6.36%)    |

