| Subjects whose index event was either unprovoked OR provoked with a risk for recurrence as described in the eligibility checklist                                                                                                                                                                                                                                                                                                                                                                    | N/A                                                                                                                                                                                                                                                         |                                                                                                                                                                                                                                                                                  |                                                                                                                                                                                                                                                                                                                                                                                                                                                                                                                    |

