| Subjects with a provoked index event without the existence of a persistent risk factor for recurrence as described in the eligibility checklist                                                                                                                                                                                                                                                                                                                                                      | N/A                                                                                                                                                                                                                                                         |                                                                                                                                                                                                                                                                                  |                                                                                                                                                                                                                                                                                                                                                                                                                                                                                                                    |

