| Systemic embolism; n (%)                                                          | 28 (1.9%)           | 47 (1.7%)           | 0.02        | 52 (2.1%)           | 73 (1.9%)           | 0.01          | 76 (1.5%)       | 58 (1.7%)       | -0.02        | 156 (1.7%)        | 178 (1.8%)        | -0.01   |         |      |
| DVT; n (%)                                                                        | 861 (58.5%)         | 1,392 (50.0%)       | 0.17        | 1,610 (65.3%)       | 1,981 (51.1%)       | 0.29          | 2,794 (56.1%)   | 1,519 (44.6%)   | 0.23         | 5265 (59.0%)      | 4892 (48.6%)      | 0.21    |         |      |
| Post-thrombotic syndrome; n (%)                                                   | 0 (0.0%)            | ** (0.1%)           | #DIV/0!     | ** (0.1%)           | ** (0.2%)           | #DIV/0!       | 131 (2.6%)      | 41 (1.2%)       | #DIV/0!      | ** (0.1%)         | ** (0.2%)         | 0.04    |         |      |
| PE; n (%)                                                                         | 1,472 (100.0%)      | 2,783 (100.0%)      | #DIV/0!     | 2,457 (99.7%)       | 3,874 (100.0%)      | -0.08         | 4,964 (99.6%)   | 3,400 (99.8%)   | -0.04        | 8893 (99.7%)      | 10057 (99.9%)     | -0.04   |         |      |
| Coagulation defects; n (%)                                                        | 28 (1.9%)           | 42 (1.5%)           | #DIV/0!     | 83 (3.4%)           | 99 (2.6%)           | #DIV/0!       | 0               | 0               | #DIV/0!      | 83 (3.4%)         | 99 (2.6%)         | 0.27    |         |      |
| Diabetes: 1 inpatient or 2 outpatient claims within 183 days; n (%)               |                     |                     |             |                     |                     |               |                 |                 |              |                   |                   |         |         |      |
| 217 (14.7%)                                                                       | 446 (16.0%)         | -0.04               | 383 (15.5%) | 574 (14.8%)         | 0.02                | 1,134 (22.8%) | 694 (20.4%)     | 0.06            | 1734 (19.4%) | 1714 (17.0%)      | 0.06              |         |         |      |

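### The propensity score has no covariate for VTE before the qualifying episode and at best a non-specific one for thrombophilia, so residual confounding of unknown direction is possible

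*Combined protocol and SAP*

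**What the plan says.** Appendix A lists two AMPLIFY criteria on risk of recurrence. One is the inclusion criterion "Subjects whose index event was either unprovoked OR provoked with a risk for recurrence as described in the eligibility checklist"; the other excludes "Subjects with a provoked index event without the existence of a persistent risk factor for recurrence". Both are marked N/A.

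Confounding control therefore rests on matching. Section 6.2 names age, sex and the comorbidity index for feasibility work and says "Remaining covariates are defined only after the study has passed the initial feasibility analysis" and the power review, pointing to Table 1 in Appendix B. Section 9 adds: "The PS should include the complete list of covariates". Table 1 is thus the full adjustment set.

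Section 5.2 says that new use "is defined as no use of either therapy in the 180 days prior to index date". In Appendix A the qualifying DVT or PE is "Measured 180 days prior to and including day of drug initiation in any diagnosis position and in an inpatient or ED care setting".

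Table 1 has rows for DVT, PE, post-thrombotic syndrome and coagulation defects. No row records a VTE before the qualifying one.

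**The concern.** The primary outcome is recurrent VTE or VTE-related death. I take it as a clinical premise, not as something the documents state, that a patient's own earlier VTE is prognostic for recurrence. It could plausibly also influence whether a prescriber starts warfarin or apixaban. The 180-day washout allows a patient anticoagulated for an earlier VTE, and off both drugs for longer than that, to enter as a new user, so such patients can be in the cohort. A factor tied to both outcome and treatment, and absent from the score, can leave the matched hazard ratio confounded. That matters twice here: for the non-inferiority comparison with 1.80, and for agreement with the trial's 0.84.

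**Working it through.** **1. Can an existing row stand in for previous VTE?** (Appendix B, matched, pooled, 3,570 per arm)

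- *PE*: 3,563 warfarin and 3,566 apixaban. Only 7 and 4 patients lack the flag, so it cannot separate patients.
- *DVT*: 1,838 (51.5%) and 1,836 (51.4%). It varies, but eligibility is read over the 180 days up to and including initiation, so the flag cannot distinguish an earlier DVT from the index event.
- *Post-thrombotic syndrome*: at most 0.2% in any arm of any database after matching, too rare to represent everyone with an earlier VTE.

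None of the three does the job.

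**2. Does *Coagulation defects* cover thrombophilia?** The only code list shown under that name is the Appendix A exclusion for hemorrhagic tendencies and blood dyscrasias: ICD-9 286.x and ICD-10 D65 to D69, including all of D68. I assume the D68 block holds some clotting disorders beside bleeding disorders. The covariate's own list is not displayed.

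Standardized difference = (p_warf − p_apix) / √{[p_warf(1−p_warf) + p_apix(1−p_apix)]/2}, recomputed because the database columns print division errors or are displaced:

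| | Unmatched | Std. diff. | Matched | Std. diff. |
|---|---|---|---|---|
| Optum | 28/1,472 vs 42/2,783 | 0.03 | 1.6% vs 2.2% | −0.04 |
| MarketScan | 83/2,464 vs 99/3,874 | 0.05 | 35/1,381 vs 40/1,381 | −0.02 |
| Medicare | 0 vs 0 | undefined | 28/1,699 vs 32/1,699 | −0.02 |

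The matched patients are drawn from the unmatched cohort, so Medicare cannot go from 0 vs 0 to 28 vs 32. The pooled columns only repeat the MarketScan counts.

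**3. The plan's own figure.** Section 10, pooled: expected events D = 7,140 × 13.74/1,000 = 98.1036. Power = Φ[√(D/4) × ln(1.8/0.84) − 1.960] = Φ[4.952 × 0.7621 − 1.960] = Φ(1.814) = 0.9652, as stated. Confounding moves the estimate rather than D, so this figure neither supports nor removes the concern. It does give SE(log HR) ≈ 2/√98.1 = 0.202, a 95% interval of a factor 1.49 each way.

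**4. Illustrative size.** The documents give no prevalence of previous VTE by arm and no effect on recurrence. Assume a prevalence of 10–30%, a 5–15 point difference between arms remaining after matching in either direction, and a relative hazard RR of 1.5–3.

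Bias factor = [1 + p_apix(RR − 1)] / [1 + p_warf(RR − 1)]

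| p_apix, p_warf | RR 1.5 | RR 2 | RR 3 |
|---|---|---|---|
| 0.10, 0.15 | 0.977 | 0.957 | 0.923 |
| 0.10, 0.20 | 0.955 | 0.917 | 0.857 |
| 0.15, 0.30 | 0.935 | 0.885 | 0.812 |
| 0.15, 0.10 | 1.024 | 1.045 | 1.083 |
| 0.20, 0.10 | 1.048 | 1.091 | 1.167 |
| 0.30, 0.15 | 1.070 | 1.130 | 1.231 |

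The extremes are 1.3/1.6 = 0.8125 and 1.6/1.3 = 1.231. With equal prevalence the factor is 1.

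**5. Consequence at the extremes.**

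- True HR 0.84 is expected to read 0.84 × 0.8125 = 0.68 or 0.84 × 1.231 = 1.03. The chance of meeting the margin, Φ[ln(1.8/HR_obs)/0.202 − 1.960], is 99.8% or 78%.
- True HR 1.00: the expected upper limit of 1.49 becomes 1.21 or 1.83.
- True HR 1.80: the one-sided error, Φ[−ln(factor)/0.202 − 1.960], goes from 2.5% to about 18% or about 0.1%.

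**The case against.** The case against has real substance.

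- **The quoted criteria do not mention previous VTE or thrombophilia.** They concern provoked status and a checklist not reproduced in the plan. Dropping an eligibility rule for both arms changes the population and does not by itself confound. This stands: the N/A entries are context, and the gap is the covariate list. The reason for N/A may also have been carried by the table's colour key, so its absence from the text should not be held against the plan.
- **Other determinants are handled.** Table 1 has cancer, hormone use, obesity and fractures. Head or major trauma and major surgery within 60 days, and pregnancy within 180 days, are exclusions. A reader might infer that the major determinants of recurrence are uncontrolled; that would be wrong.
- **Thrombophilia may be partly covered.** A reader might infer that no covariate touches it. The documents do not show that, because the one list displayed takes the whole D68 block. But balance on a category mixing bleeding and clotting codes, with impossible Medicare counts, does not establish balance on thrombophilia.
- **Modest bias need not change the conclusion.** At a true HR of 0.84 the expected upper limit is 0.84 × 1.49 = 1.25, and even the worst upward factor takes it only to 1.54. This stands for the non-inferiority verdict at that value. It does not cover a true HR nearer the margin, or agreement with the trial's point estimate.

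**Conclusion.** The gap is real and worth closing: the score has no measure of VTE before the qualifying episode, and thrombophilia is captured at best non-specifically. Residual confounding is possible. It is not demonstrated, because nothing in the documents shows that either factor differs between arms or drives drug choice.

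A reader might infer that the omission favours apixaban and is anti-conservative. That holds only if previous VTE remains more common on warfarin after matching. The one row that might suggest this is post-thrombotic syndrome in unmatched Medicare (131/4,983 vs 41/3,406, standardized difference 0.10). It sits among visibly misplaced Medicare entries: the immobilization cells repeat the CHA2DS2-VASc means, and the antibiotics cells repeat the combined diuretic counts. I would not rest a direction on it.

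The factor of 0.81 to 1.23 comes entirely from the assumed prevalences and relative hazards. It could be 1.

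**What to change.** Before Section 13 is run, add to Section 6.2, Table 1 and the propensity score:

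1. **Previous VTE**: a personal-history-of-VTE diagnosis code in the fixed 180-day baseline. As a sensitivity definition, add VTE codes from all available look-back before that baseline. Keep this secondary, because look-back is uneven. Unmatched means are about 1,696 and 1,675 days in Optum (warfarin, apixaban), 2,110 and 2,106 in MarketScan, and 651 and 703 in Medicare. The Medicare arms still differ after matching (720 and 682).
2. **Thrombophilia or hypercoagulable state**: a specific indicator, separate from the bleeding-tendency codes. Show the code list behind *Coagulation defects* and correct its Medicare counts.

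Report standardized differences for both before and after matching, and repeat the match in each database.

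The cost is a small amount of programming and a possible change in the matched 7,140, in which case the Section 10 power tables need updating. No new data source is needed. If the new covariates prove balanced, the concern about these two factors is largely answered, as far as claims codes can measure them.
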